Title: High flow nasal cannula compared to continuous positive airway pressure in the treatment of obstructive sleep apnea

Investigator: [name]

Official Title: Director of Sleep Center

NCT number: NCT03843372

Document date: June 08, 2020

Materials and Methods

This work was approved by the institutional review board of Chang Gung Memorial Hospital (201601844B0C101), and all subjects signed informed consent forms in accordance with the amended Declaration of Helsinki. Subjects who were diagnosed with OSAHS via standard polysomnography (PSG) were recruited in the sleep center of Chang Gung Memorial Hospital. The definition of OSAHS was an AHI greater than 5 times per hour (times/hr). Patients with central sleep apnea, hypoventilation syndrome, chronic obstructive airway disease, an unstable hemodynamic state, who were younger than 18 years old, with an Eastern Cooperative Oncology Group Performance Status higher than grade 2, who experienced intolerance to HFNC or CPAP, and pregnant women were excluded. In addition, patients who recently underwent surgery or used an oral appliance were also excluded.

Study Protocols

This was a prospective crossover study. All of the participants were randomized into two groups for minimized first night effects. All of them would receive one-night HFNC therapy and another night for CPAP titration under PSG monitoring. The duration between these two treatments was approximately one week apart. The first group underwent CPAP titration on the first night and HFNC titration on the second night. Conversely, the second group was subjected to HFNC on the first night and CPAP titration on the second night. All of the participants were asked and recorded their side effects following completion of an HFNC or CPAP.

Polysomnography and scoring methods

Standard overnight PSG included recording electroencephalography, bilateral electroculograms, submental electromyogram, electrocardiography, nasal pressure, oronasal thermistor, oximetry, chest, and abdominal movement (inductance plethysmography), body position, sound intensity, and bilateral tibia electromyogram. All signal results for each night were collected and digitized on a computerized PSG system (Embla N7000, USA; Compumedics, Australia). Sleep stages and respiratory events were scored according to the American Academy of Sleep Medicine (AASM, Version 2.4; 2017) scoring manual.

CPAP titration

All patients underwent a nasal CPAP titration study in the sleep laboratory for an entire night. During the CPAP titration study, manual CPAP titration was conducted to determine the optimal CPAP level required. A CPAP interface was individually fitted from a wide range of interfaces to maximize comfort and minimize leaks. The preparation of the patients was accomplished by a trained PSG technician who supervised the study. All of the participants used a CPAP mask and machine (System one, Philip Respironic, US) throughout the study. Preparation of the patients was accomplished by the technician who supervised the study and corrected the mask position and fitting initially. All of the patients were started at a low pressure (4 cm H₂O) initially, and then the pressure was manually increased after the patients went to sleep. The pressure sensor was used to evaluate apneas, hypopneas, and flow limitations. The optimal CPAP pressure was determined to be the pressure that could eliminate apnea, hypopnea, desaturation, and snoring in a supine position or when possible in REM sleep [18].

High flow titration

All participants underwent high flow titration in the sleep laboratory for an entire night. An air compressor (AIRVOTM2, Fisher & Paykel Healthcare, Auckland, New Zealand) delivered the airflow via nasal cannula (Optiflow). A heating tube (900PT500) and humidifier kept the temperature at 34–37°C and absolute humidity of 44mg/L. The initial flow rate was set as 20L/min. After the patients fell asleep, the flow rate was increased by 10L/min up to a maximum of 60L/min to try to eliminate apneas, hypopneas, and desaturation in the supine position or REM sleep. This principle was similar to the CPAP titration; however, RIP signals were used to distinguish the respiratory events. If the participants became awake or complain that the flow rate was too high or uncomfortable, the flow rate would be decreased 10 L/min until they could return to sleep. When the subject fell asleep again, the flow rate would be increased again to try and discover the optimal flow rate that could maintain sleep and achieve a favorable AHI reduction. The flow rate that could maintain sleep, plus the best AHI was defined as the optimal flow rate. Once the optimal flow rate was determined, the subjects were allowed to sleep at that flow rate for the rest of the night.

Statistical analysis

The most of respiratory event and sleep quality parameters were not normal distribution. Therefore, the carry over effect of CPAP and HFNC were evaluated by Wilcoxon rank sum test. The AHI, desaturation index, sleep efficiency, and total sleep time between CPAP titration, and HFNC were also compared with the Wilcoxon rank sum test. The side effects of HFNC and CPAP were compared with the chi-square test and Fisher's exact probability test. A p-value < 0.05 was considered statistically significant. Statistical evaluations were performed using the SPSS 16.0 Software (SPSS Inc., Chicago, Ill). Data were presented as median \pm interquartile range (IQR). P-values < 0.05 were considered to be statistically significant.

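### Does the undated intolerance exclusion confine the side-effect comparison to patients who tolerated both devices?

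*Combined protocol and SAP*

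**What the plan says.** All references are to the combined protocol and SAP.

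- **Materials and Methods** excludes patients "who experienced intolerance to HFNC or CPAP, and pregnant women were excluded". The clause carries no time limit.
- **Study Protocols** describes a randomised two-night crossover: "All of them would receive one-night HFNC therapy and another night for CPAP titration under PSG monitoring". On side effects it says: "All of the participants were asked and recorded their side effects following completion of an HFNC or CPAP".
- **CPAP titration**: "All patients underwent a nasal CPAP titration study in the sleep laboratory for an entire night".
- **High flow titration**: "All participants underwent high flow titration in the sleep laboratory for an entire night". It foresees discomfort ("If the participants became awake or complain that the flow rate was too high or uncomfortable") and answers it by adjusting the device: "the flow rate would be decreased 10 L/min until they could return to sleep".
- **Statistical analysis**: "The side effects of HFNC and CPAP were compared with the chi-square test", with Fisher's exact test also named. It states no analysis set, no denominator and no rule for a night that ends early.

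**The concern.** Intolerance and side effects are close to the same thing. If a patient who fails a device on a study night is excluded afterwards, or if that night yields no side-effect record, the most affected patients leave the comparison because of the outcome being compared.

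Two features of the text invite the worry. First, the exclusion is undated and names HFNC, yet the documents describe no HFNC exposure before the study night, so one may ask when such intolerance could have arisen. Second, side effects are asked about once the treatment is complete and each treatment is described as a full night, so a night cut short might contribute nothing.

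The side-effect rate on the less tolerable device would then tend to be too low, and the difference between devices could be hidden, created or exaggerated. The two routes also act differently. Exclusion takes a patient out of both devices; an unrecorded night takes the patient out of one, so the devices would be compared in partly different people.

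**Working it through.** The plan states no intolerance rate, side-effect rate or sample size, so there is no figure to reproduce. The check is first a reading of the text and then an illustration of what the adverse reading would cost.

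**Exclusion route, from the text**

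1. The clause stands mid-list, between performance status and pregnancy, in a list that also covers age, central sleep apnea and chronic airway disease. None of these is expressly limited to the time before randomisation; an eligibility list implies it.
2. The list precedes the Study Protocols heading, where randomisation first appears.
3. The list does put a time word on surgery (recent), but that sets a look-back window. It does not separate events before randomisation from events after it. A history of intolerance needs no such window.
4. Study Protocols then has every participant randomised, receiving both nights and asked about side effects. High flow titration keeps an uncomfortable patient in the study by lowering the flow.
5. The lack of described earlier HFNC exposure is weak evidence the other way, because the whole text is very short.

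**Completion route, from the text**

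1. Study Protocols says when the question was put. It does not say that this was the sole collection point, and completion can mean the end of a session, even a shortened one.
2. Both titration sections say every patient had a full night. The documents describe no stopped night.
3. If a night were lost, the patient would still contribute the other one, so the comparison would not shrink to patients tolerant of both devices.

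**Size under the adverse reading (all rates assumed)**

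Let h and c be the shares intolerant of HFNC only and of CPAP only, with no overlap. Let bH and bC be the side-effect rates in tolerant patients. Suppose every intolerant patient has a side effect on the offending device, and that intolerance of one device is unrelated to side effects on the other. Then:

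- true HFNC rate = h + (1 − h)·bH
- true CPAP rate = c + (1 − c)·bC
- rates read after exclusion: bH and bC

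| h, c | bH, bC | True HFNC vs CPAP | True difference | Difference read | Change (points) |
|---|---|---|---|---|---|
| 15%, 5% | 30%, 30% | 40.5% vs 33.5% | +7.0 | 0 | 7.0 |
| 15%, 5% | 30%, 37.4% | 40.5% vs 40.5% | 0 | −7.4 | 7.4 |
| 15%, 5% | 20%, 40% | 32.0% vs 43.0% | −11.0 | −20.0 | 9.0 |
| 5%, 2% | 30%, 30% | 33.5% vs 31.4% | +2.1 | 0 | 2.1 |
| 5%, 2% | 30%, 32.1% | 33.5% vs 33.5% | 0 | −2.1 | 2.1 |
| 5%, 2% | 20%, 40% | 24.0% vs 41.2% | −17.2 | −20.0 | 2.8 |

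First row: 0.15 + 0.85 × 0.30 = 0.405 and 0.05 + 0.95 × 0.30 = 0.335.

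For a device with intolerance i and tolerant rate b, the understatement is i·(1 − b). If intolerant patients had side effects at rate s instead of always, it would be i·(s − b). Setting s = 1 therefore gives the largest value for a given i and b.

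Under these assumptions the completion route gives the same readings. The routes part when the devices are related. Take h = 15%, c = 0, and CPAP side effects in 10% of HFNC-intolerant patients against 30% of the rest. The true CPAP rate is 0.85 × 0.30 + 0.15 × 0.10 = 27.0%. It reads 30.0% after exclusion, but 27.0% if only the HFNC night is lost.

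Under the prior-history reading, with every started night recorded, no one leaves after randomisation and each understatement is zero.

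**The case for a change.** The strongest case for a change is that the reader cannot tell which rule was applied. The exclusion is undated, the collection point is tied to completion, and the analysis section names no denominator. High flow titration foresees discomfort but does not say how a patient who still cannot continue is counted, and CPAP titration describes no step for discomfort at all. The phrase covering all participants does not settle it, since someone excluded for intolerance may no longer count as a participant. The selection would act directly on the outcome, and a clarifying sentence costs almost nothing.

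The silence on timing and denominator is real, and that part stands. The step from silence to bias does not. It requires either reading an eligibility criterion as a rule for removal after randomisation, against its placement, or supposing stopped nights that the text does not mention and, taken at face value, rules out.

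The illustrations add no evidence either way. One set of assumed intolerance rates yields a hidden, a created or an inflated difference according to the side-effect rates chosen, so they show possibility only.

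Rewording eligibility would also probably come too late. The methods are written in the past tense and the statistical section describes distributions as already seen, so new wording would not alter who was entered.

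**Conclusion.** No change to the plan is called for. This is a gap in detail that analysts fill sensibly. Followed in its ordinary sense, with intolerance as a baseline exclusion and side effects asked of everyone after each night, the plan gives a side-effect comparison free of this selection.

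The conclusion rests on two assumptions: that the exclusion was applied before randomisation, as its place in the list implies, and that every night started was recorded. If either failed, side-effect rates could be understated. In the illustrations the difference between devices moves by 2.1 to 2.8 points at 5% and 2% intolerance, and by 7.0 to 9.0 points at 15% and 5%. All of those rates are assumed, and the documents show neither the size nor the direction of any real effect. An ordinary account of patient flow and of the number of nights behind each side-effect rate would show which case applied.

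### The order of devices is randomised because a first-night effect is expected, but the device comparison uses neither night nor order, so such an effect costs power and, if the order groups are unequal, shifts the estimate

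*Combined protocol and SAP*

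**What the plan says.** The Study Protocols section describes a two-night, two-order crossover: "This was a prospective crossover study". One group took CPAP first: "The first group underwent CPAP titration on the first night and HFNC titration on the second night". The other took the reverse order: "Conversely, the second group was subjected to HFNC on the first night and CPAP titration on the second night". On spacing, it says: "The duration between these two treatments was approximately one week apart". The stated purpose of the randomisation is to deal with a night effect: "All of the participants were randomized into two groups for minimized first night effects". No allocation ratio, blocking or group size is given.

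The Statistical analysis section names three analyses:

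- Carry-over: "the carry over effect of CPAP and HFNC were evaluated by Wilcoxon rank sum test".
- Device comparison: "The AHI, desaturation index, sleep efficiency, and total sleep time between CPAP titration, and HFNC were also compared with the Wilcoxon rank sum test".
- Side effects: "The side effects of HFNC and CPAP were compared with the chi-square test and Fisher's exact probability test".

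It mentions no test for a night effect, no night or order term, and no stratification by randomised order.

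**The concern.** Randomising the order spreads a night effect over both devices. It does not remove the effect from an analysis that sorts the recordings by device alone. The plan expects such an effect, builds the design around it, and then leaves out of the device comparison the one variable that would take it out.

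Two things are at stake. If the two order groups differ in size, part of the night effect is counted as a device effect. If they are equal, it cancels from the mean but remains as extra scatter, and the comparison is weaker than the design allows. Sleep efficiency and total sleep time, two of the four compared outcomes, are where one would expect a first-night effect to act most directly.

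The carry-over test does not cover this. It asks whether the first device still acts on the second night. It neither estimates a night effect nor adjusts the device comparison for one.

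**Working it through.** The documents give no sample size, SD, effect size or power, so there is no figure of the plan's own to reproduce. The algebra follows from the design; all numerical inputs are assumptions.

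**Set-up.** Let D = HFNC minus CPAP within a patient, with SD σ; τ = device effect; π = night 2 minus night 1; n1 = CPAP-first patients; n2 = HFNC-first patients; N = n1 + n2.

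- CPAP-first: mean D = τ + π.
- HFNC-first: mean D = τ − π.
- Ignoring order: mean D = [n1(τ + π) + n2(τ − π)]/N = τ + π(n1 − n2)/N.
- With n1 = n2 the shift is zero, but half the patients are centred at τ + π and half at τ − π, so the variance of D is σ² + π².

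**Using order.** Take night 2 minus night 1 for each patient. Its mean is π + τ in the CPAP-first group and π − τ in the HFNC-first group. The groups differ by 2τ. The night effect cancels whatever the group sizes, and half the difference is the device effect.

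**Equal groups, closed form.** Take a paired comparison with 80% power when π = 0 (two-sided 5%). With π present, power = Φ[(1.96 + 0.84)/√(1 + π²/σ²) − 1.96].

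| π/σ | Variance multiplier | Power |
|---|---|---|
| 0.25 | 1.0625 | 77.6% |
| 0.5 | 1.25 | 70.7% |
| 1.0 | 2.0 | 50.8% |

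**Equal groups, simulation.** Assumed: N = 30 split 15:15, σ = 10, τ = 6, within-patient correlation 0.5, normal data. Power:

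| π | Planned rank sum by device | Signed-rank on D | Rank sum of night differences between order groups |
|---|---|---|---|
| 0 | 63% | 86% | 85% |
| 5 | 60% | 80% | 86% |
| 8 | 54% | 69% | 86% |

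At π = 2.5 the loss from the night effect is negligible. In the π = 0 row the gap between the planned test and the other two comes from ignoring the pairing, which is a separate defect. The night effect's own cost is read down a column: at π = 8 it is 63 − 54 = 9 points for the planned test and 86 − 69 = 17 points for a signed-rank test. Pairing the test without using order therefore leaves the night effect in place.

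**Unequal groups.** Same N and σ, no device difference (τ = 0), split 20:10, π = 8.

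- Shift: 8 × (20 − 10)/30 = 2.7 points.
- Type I error of the planned test: about 21%, 7% or 2% at within-patient correlation 0, 0.5 or 0.7.
- Type I error of a signed-rank test, which the plan does not name: about 15%.
- Type I error of the order-based test: 4 to 5%.

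A split of 20:10 or worse has probability 2 × P(X ≤ 10), X ~ Binomial(30, 0.5), which is 0.099 under simple randomisation. At 18:12 the shift is 8 × 6/30 = 1.6 points and the signed-rank type I error stays near 5%.

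**The case against.** The case for leaving the analysis alone has five parts.

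- **The text does not state what is ranked.** The remedy is itself a rank sum test, so it could be argued that the plan already means it. This does not fit the wording, which places the comparison between the two devices and not between the two order groups.
- **The bias is conditional.** Over repeated 1:1 randomisations the shift averages to zero, and a signed-rank test keeps a type I error of about 5% overall. This is correct. But a trial has one realised split, and its estimate carries that split's shift.
- **The planned test is conservative under positive within-patient correlation.** Much of the false-positive excess then disappears. This also stands, but the estimate remains shifted and power is lower still.
- **The night effect may be small.** Patients had already been diagnosed by polysomnography, so the study nights were not their first recordings, although the place and timing of the diagnostic night are not given. At π/σ = 0.25 the closed-form loss is only 2.4 points (80 − 77.6).
- **Using order has a price** if there is no night effect (see the fix).

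A reader might go further and infer that the device comparison is biased, or that its false-positive rate is well above 5%. The documents do not support that. They do not say the groups were unequal, give no size for the night effect, and give no within-patient correlation. The larger error rates above need a large imbalance, a large night effect and, for the planned test, a low correlation.

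**Conclusion.** The point holds as an inefficiency with a conditional risk of bias. The plan anticipates a night effect and leaves it in the device comparison and in the side-effect comparison. The algebra depends only on the design.

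The firmer consequence is lost power: under the assumed values, about 9 points for the planned test and 17 for a signed-rank test at π = 8, and next to nothing at π = 2.5. The shift of π(n1 − n2)/N arises only if the realised order groups differ in size, which the documents leave open. All percentages rest on assumed values and on normal data, whereas the plan says most parameters were not normally distributed, so they indicate scale only. The change should be made, but the point does not by itself invalidate the comparison.

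**What to change.** In the Statistical analysis section, replace the device comparison with one built on the randomised groups. For each patient and outcome, take night 2 minus night 1; compare these differences between the CPAP-first and HFNC-first groups with the Wilcoxon rank sum test; report half the Hodges-Lehmann shift, with its confidence interval, as the HFNC minus CPAP effect. For side effects, use the order-adjusted paired test (Mainland-Gart). State the number of patients in each order group.

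This also repairs the pairing, stays with the test the plan already names, and needs no new data provided the randomised order was recorded for each patient. It takes a short wording change and a rerun. The document is written in the past tense, so no change to the allocation is proposed.

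The cost falls where there is no night effect: about 1 to 2 points of power against a signed-rank test with equal groups, and about 6 points at 20:10. Against the planned test, the assumed equal-group case shows a gain even then (85% against 63%), because the pairing is used.

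### As written, the CPAP–HFNC comparison uses an unpaired rank sum test on two nights from the same patients, so its p-values are miscalibrated and the crossover's power gain is lost

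*Combined protocol and SAP*

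**What the plan says.** The Study Protocols section of the combined protocol and SAP sets out a two-period, two-sequence crossover: "This was a prospective crossover study". Every participant gets both treatments: "All of them would receive one-night HFNC therapy and another night for CPAP titration under PSG monitoring". The sequences are CPAP then HFNC ("The first group underwent CPAP titration on the first night and HFNC titration on the second night") and the reverse ("the second group was subjected to HFNC on the first night and CPAP titration on the second night"). On spacing it says: "The duration between these two treatments was approximately one week apart".

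The Statistical analysis section justifies rank methods by non-normality: "The most of respiratory event and sleep quality parameters were not normal distribution". It uses one named test for two purposes. The first is carry-over: "the carry over effect of CPAP and HFNC were evaluated by Wilcoxon rank sum test". The second is the treatment comparison: "The AHI, desaturation index, sleep efficiency, and total sleep time between CPAP titration, and HFNC were also compared with the Wilcoxon rank sum test". The significance threshold is 0.05, with sidedness not stated. The section names no signed-rank test, within-patient difference, period adjustment or other paired method. It gives no sample size, power, expected effect or between-night correlation.

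**The concern.** The rank sum test treats the CPAP values and the HFNC values as coming from two separate sets of people. Here they come from the same people, so the test uses the wrong variance for the difference. Non-normality is a reason to use ranks; it is not a reason to drop the pairing.

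A rank sum test does have a proper place in an AB/BA crossover, where it compares within-patient period differences between the two randomized sequences. The plan's sentence does not describe that. It compares the outcomes themselves by treatment.

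All four efficacy and sleep-quality p-values (AHI, desaturation index, sleep efficiency, total sleep time) depend on this test. With positive within-patient correlation, real differences are missed more often than they need be. In a head-to-head comparison with no stated margin, a missed difference could be read as HFNC performing like CPAP. The planned summaries are medians with interquartile ranges, with no interval for the within-patient difference, so a reader could not see the problem in the report.

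**Working it through.** The documents give no sample size or power figure to reproduce. The check therefore asks what the test choice does under stated assumptions.

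**Inputs**
- From the documents: crossover design with one night per treatment per patient; rank sum test by treatment; alpha 0.05.
- Assumed: two-sided testing; correlation ρ between a patient's two nights of 0.3, 0.5 or 0.7, with 0 and negative values as limiting cases; 20, 30 or 50 patients; log-normal outcomes; a shift of 0.5 SD on the log scale where an effect is needed.

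**Step 1: true size.** With n patients and common SD σ, the mean difference has variance 2σ²(1−ρ)/n. An unpaired test takes it to be 2σ²/n, so it rejects only when the correctly scaled statistic exceeds 1.96/√(1−ρ):

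size = 2 × [1 − Φ(1.96/√(1−ρ))]

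| ρ | 1.96/√(1−ρ) | True size |
|---|---|---|
| 0 | 1.960 | 5.0% |
| 0.3 | 2.343 | 1.9% |
| 0.5 | 2.772 | 0.6% |
| 0.7 | 3.578 | 0.03% |
| −0.2 | 1.789 | 7.4% |
| −0.3 | 1.719 | 8.6% |

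**Step 2: power when a paired test has 80%.** The correctly scaled statistic then has mean 1.960 + 0.842 = 2.802, and unpaired power = Φ(2.802 − 1.96/√(1−ρ)):
- ρ = 0.3: Φ(0.459) = 68%
- ρ = 0.5: Φ(0.030) = 51%
- ρ = 0.7: Φ(−0.777) = 22%

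Holding paired power at 80% means the true effect shrinks as ρ rises. At n = 30 it is 2.802 × √(2(1−ρ)/30) = 0.61, 0.51 and 0.40 SD. A simulation on the same footing (n = 30, 20,000 runs) gave signed-rank power of about 75% and rank sum power of 63%, 47% and 21%.

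**Step 3: effect fixed at 0.5 SD.** This simulation used 10,000 log-normal data sets per row. The signed-rank test was applied to within-patient log differences. The period-difference test is the rank sum on night 1 minus night 2 log differences between sequences. Each cell shows size / power.

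| n | ρ | Unpaired rank sum | Signed-rank | Period-difference rank sum |
|---|---|---|---|---|
| 20 | 0.3 | 0.021 / 0.30 | 0.052 / 0.41 | 0.043 / 0.39 |
| 20 | 0.5 | 0.009 / 0.27 | 0.051 / 0.54 | 0.047 / 0.51 |
| 20 | 0.7 | 0.001 / 0.25 | 0.050 / 0.76 | 0.044 / 0.74 |
| 30 | 0.3 | 0.019 / 0.44 | 0.046 / 0.59 | 0.043 / 0.57 |
| 30 | 0.5 | 0.005 / 0.44 | 0.047 / 0.73 | 0.044 / 0.72 |
| 30 | 0.7 | 0.001 / 0.44 | 0.048 / 0.92 | 0.043 / 0.91 |
| 50 | 0.3 | 0.020 / 0.71 | 0.048 / 0.82 | 0.047 / 0.81 |
| 50 | 0.5 | 0.006 / 0.74 | 0.045 / 0.92 | 0.043 / 0.92 |
| 50 | 0.7 | 0.000 / 0.78 | 0.050 / 0.99 | 0.048 / 0.99 |

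Both paired analyses hold their size. At n = 30 the unpaired test stays at about 44% power while the paired tests climb with ρ. At ρ = −0.3 and n = 30 the unpaired test had size 0.080, against 0.051 for signed-rank.

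**Step 4: the same loss in patients.** For 80% power at 0.5 SD, a paired analysis needs 2(1−ρ)(2.802/0.5)² patients: 44, 32 and 19 at ρ = 0.3, 0.5 and 0.7. With ρ = 0, as an independent-samples calculation assumes, the figure is 63 values per treatment.

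**The case against.** The strongest reply is that the section is short and loosely worded, and that rank sum may be a slip for signed rank. The documents cannot rule that out, so the sponsor should confirm what was run. But the plan names the rank sum test twice, and the treatment comparison is explicitly tied to the test used for carry-over. Even if it is a slip, the text specifies the wrong test and must be corrected.

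Several limits on the harm do stand:
- With positive correlation the test is conservative, so a significant result is not undermined and a very large difference would probably still be detected.
- At ρ = 0 there is no miscalibration. CPAP is titrated to abolish events, so AHI on CPAP may sit near a floor and correlate only weakly with AHI on HFNC. One correlation need not suit all four outcomes.
- Inflated error needs negative correlation, for which the documents give no reason.
- The 68%, 51%, 22% series reflects an effect that shrinks by construction. At a fixed effect the unpaired test forgoes a gain; its power does not collapse.
- The documents make no equivalence claim, so the risk of misreading a null result is a matter of interpretation.

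Two technical points are also fair. A rank sum comparison of first-night values between sequences would be valid, though inefficient; it is not what the plan describes. And a plain signed-rank test does not adjust for night order, which the design randomizes because of first-night effects. In simulations with 30 patients split 18/12 and a 0.4 SD period effect, signed-rank size stayed at 3–6%, so this is a reason to consider the period-difference version rather than an obstacle to the fix.

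**Conclusion.** The concern holds. As written, the test contradicts the design: it is an independent-samples test on paired nights, and it governs all four PSG comparisons. The p-values are miscalibrated unless the two nights are uncorrelated. For correlations of 0.3 to 0.7 the nominal 5% level falls to between 1.9% and 0.03%. With 30 patients and a 0.5 SD effect, power is about 44% where a paired analysis would give roughly 57–92%. These sizes depend on assumed correlation, sample size, effect and distribution, because the documents state none of them. The mismatch between test and design does not depend on those assumptions. The use of the rank sum test for carry-over is not at fault, since that comparison can properly be made between the sequence groups. This must be fixed before the treatment p-values are relied on, above all any non-significant one.

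**What to change.** 1. Confirm which test was actually run.
2. For AHI, desaturation index, sleep efficiency and total sleep time, replace the rank sum test with the Wilcoxon signed-rank test on each patient's HFNC minus CPAP difference. State the scale of the difference (raw or log), because the signed-rank result depends on it.
3. Report the Hodges–Lehmann median within-patient difference with a 95% confidence interval for each outcome.
4. If the rank sum test is kept, or if allowance for night order is wanted, apply it to night 1 minus night 2 differences compared between the two sequence groups, and say so explicitly.

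The side-effect comparison deserves the same look: chi-square and Fisher's tests also assume independent groups, and a paired method such as McNemar's test would fit data from the same patients.

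The cost is a change of wording and a re-run on the data already collected. No patients or procedures are added. If a signed-rank test was in fact used, only the wording and the added interval are needed.

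### Side effects of the two devices come from the same patients but are compared with chi-square and Fisher tests for independent groups, so the p-values ignore the pairing

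*Combined protocol and SAP*

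**What the plan says.** The Study Protocols section describes the design: "This was a prospective crossover study". It goes on: "All of them would receive one-night HFNC therapy and another night for CPAP titration under PSG monitoring", with the two nights about a week apart. On side effects it says: "All of the participants were asked and recorded their side effects following completion of an HFNC or CPAP". Read with the design, each patient gives two side-effect records, one per device.

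The Statistical analysis section then states: "The side effects of HFNC and CPAP were compared with the chi-square test", and names Fisher's exact test beside it. The threshold is p < 0.05, with sidedness not stated. No McNemar test, conditional logistic model or other paired or crossover method for binary data appears anywhere.

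The Materials and Methods section also lists, among those excluded, patients "who experienced intolerance to HFNC or CPAP".

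**The concern.** Chi-square and Fisher's exact test for a 2x2 table assume that the two columns hold different people. Here they hold the same people twice. The difference in proportions is still estimated without bias from this source, but its uncertainty is not. Chi-square uses a variance without the within-patient covariance. Fisher's test, for the same reason, refers the table to the wrong null distribution. Both also see only the marginal totals, whereas the evidence in paired binary data lies in the patients who had the effect on one device and not on the other.

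The direction of the error depends on the sign of the within-patient correlation. If patients who report a problem with one device tend to report it with the other, which is plausible but not documented, both tests are conservative and real differences are missed. If the correlation is negative, chi-square gives too many false positives. This is the only side-effect comparison of the devices that the documents plan.

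**Working it through.** **Inputs.** From the documents: the crossover design, two device nights per patient, side effects asked of everyone, chi-square and Fisher as the tests, and a 0.05 threshold. The plan has no figure of its own to reproduce: it gives no sample size, side-effect rates, correlation or recording scale. Assumed here: each side effect is recorded as present or absent; tests are two-sided; chi-square has no continuity correction; n = 30 (also 20 and 50); rates of 40% v 20%, or 30% v 30% for the null; phi from -0.2 to 0.5.

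**Step 1: variance.** With rates p1 and p2, and q = 1 - p, the variance of the paired difference is

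[p1q1 + p2q2 - 2·phi·√(p1q1·p2q2)] / n,

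while the independent-groups form stops after the first two terms. True over unpaired is therefore 1 - 2·phi·√(p1q1·p2q2)/(p1q1 + p2q2). For 40% v 20%: p1q1 = 0.24, p2q2 = 0.16, their sum is 0.40, and √(0.24 × 0.16) = 0.196.

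- phi = 0.4: 1 - 0.8 × 0.196/0.40 = 0.608, so the unpaired variance is 1/0.608 = 1.64 times the true one.
- phi = -0.2: 1 + 0.4 × 0.196/0.40 = 1.196, so it is 1/1.196 = 0.84 times the true one.

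**Step 2: power and size.** All possible paired tables for n = 30 were enumerated exactly, with rejection at p < 0.05.

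| Scenario | phi | Chi-square | Fisher | Exact McNemar | Mid-P McNemar |
|---|---|---|---|---|---|
| Power, 40% v 20% | 0.4 | 36% | 24% | 43% | 54% |
| | 0.2 | 38% | 27% | 34% | 43% |
| | 0 | 39% | 30% | 28% | 37% |
| | -0.2 | 40% | 32% | 25% | 32% |
| Size, 30% v 30% | 0.4 | 1.2% | 0.45% | 1.8% | 3.75% |
| | 0 | 4.9% | 2.6% | 2.5% | 4.4% |
| | -0.2 | 7.2% | 4.2% | 2.8% | 4.7% |

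Over n = 20, 30 and 50, mid-P size never exceeds 4.7%, while chi-square reaches 7.8% (n = 20, phi = -0.2). At phi = 0.4, chi-square v mid-P power is 23% v 32% for n = 20 and 62% v 80% for n = 50. A separate simulation with other rates (20% or 40% on both devices) agrees: at n = 30 and 20% on both, chi-square size falls from 7.1% at phi = -0.2 to 0.8% at phi = 0.5.

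**Step 3: one set of totals, different pairings.** Take 12/30 v 5/30. The planned tests give p = 0.045 (chi-square) and 0.084 (Fisher) however the answers pair up. The paired p-values depend on the discordant split:

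| Split | phi | Exact McNemar | Mid-P |
|---|---|---|---|
| 7:0 | 0.55 | 0.016 | 0.008 |
| 8:1 | 0.37 | 0.039 | 0.021 |
| 9:2 | 0.18 | 0.065 | 0.039 |
| 10:3 | 0 | 0.092 | 0.057 |
| 11:4 | -0.18 | 0.118 | 0.077 |
| 12:5 | -0.37 | 0.143 | 0.096 |

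For example, 7:0 gives 2 × (1/2)^7 = 0.016. By mid-P, Fisher misses a significant difference at 7:0, 8:1 and 9:2. Chi-square's significant result is not supported at 11:4 and 12:5, where the correlation is negative.

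With 10/30 v 4/30 both planned tests are non-significant (0.067 and 0.125). The most favourable split, 6:0, gives exact McNemar 0.031. The next, 7:1, gives 0.070 exact and 0.039 mid-P.

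**The case against.** The mismatch of test and design is hard to dispute. Chi-square could in principle mean McNemar's chi-square, but naming it beside Fisher's exact test points to the ordinary 2x2 analysis, and the text would need correcting either way. The serious objections concern weight.

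- **The size is wholly assumed.** This stands. It is certain that the tests do not fit the design; it is not certain that any conclusion changes. At phi = 0 chi-square's size is about right.
- **The error is uneven.** This stands. A clear excess of false positives arises only for chi-square with negative correlation. Fisher's size is at most 4.84% in the exact grid and 5.2% in the simulation. With positive correlation the cost is lost power.
- **The worked example mixes two effects.** This stands in part. At 10:3 phi is exactly 0, so chi-square's variance is right, and the non-significant McNemar results reflect the small-sample behaviour of a conditional test. The same is true of exact McNemar at 9:2. The 7:0 and 6:0 splits are limiting cases. The remaining rows still show that the planned p-value cannot respond to the pairing.
- **Side effects are not a named endpoint, and the pairing problem is wider.** The documents do not label side effects primary or secondary. The same section compares the sleep and respiratory measures between devices with a rank sum test, also a method for independent groups. That is a separate point; nothing here vouches for those comparisons.

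**Conclusion.** The concern holds. Following the plan gives side-effect p-values that ignore the within-patient pairing, and they are correct only if that correlation happens to be zero. Under the assumed 30 patients and present/absent recording, the consequence ranges from 18 points of power lost against mid-P McNemar (54% - 36%, chi-square at phi = 0.4; 30 points for Fisher) to a chi-square false-positive rate of 7.2% at phi = -0.2. The estimated rate difference is not affected. This should be fixed, but it is confined to the side-effect comparison. Because patients intolerant of either device are excluded, that comparison has limited scope whichever test is used.

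**What to change.** For each side effect recorded as present or absent, replace chi-square and Fisher with McNemar's test, using the mid-P version when discordant pairs are few. Report both discordant counts and the paired risk difference with its 95% confidence interval. If order is to be allowed for, the Mainland-Gart or Prescott test may be used.

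The cost is a sentence in the SAP and a re-run, provided each patient's answers for both nights were kept. There is a price in power if the correlation is not positive: at n = 30 and 40% v 20%, mid-P is about 2.5 points below chi-square at phi = 0 and about 8 points below at phi = -0.2, where chi-square's size is itself inflated. Mid-P overtakes chi-square at about phi = 0.1. Exact McNemar does so only at about 0.3, and at n = 20 not even at 0.5 (20% v 21%), which is why mid-P is preferred.
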